6.1.2 Safety Endpoints

Serious Adverse Event (SAE)

SAEs determined by the flag indicating if the adverse event is serious on the Adverse Events eCRF page will include those that occur after signing of the informed consent and up to and including end of study.

Treatment-Emergent Adverse Event

Adverse Events (AEs) recorded on the Adverse Events eCRF page that occurs on or after first dose of investigational product as determined by the flag indicating if the adverse event started prior to the first dose on the Adverse Events eCRF and up to and including 112 days after the end of investigational product (16 weeks after the last dose of IP) or end of study, whichever comes earlier.

Serious Treatment-Emergent Adverse Event

A serious treatment-emergent adverse event is an SAE considered to be treatment-emergent.

Treatment-Related Adverse Event

A treatment-related AE is defined as a treatment-emergent adverse event that is considered by investigators to have reasonable possibility that it may have been caused by IP as determined by the flag indicating if the event is caused by investigational product on the Adverse Events eCRF page.

Serious Treatment-Related Adverse Event

A serious treatment-related adverse event is an SAE considered to be treatment-related.

Columbia-Suicide Severity Rating Scale (C-SSRS)

The C-SSRS is a clinician rating of suicidal behavior and ideation. Two versions depending on the type of visits will be used in this study: Screening and Since Last Visit. The C-SSRS consists of a maximum of 20 items to evaluate suicidal behavior and suicidal ideation.

Beck Depression Inventory (BDI)-II

The Beck Depression Inventory (BDI)-II is a 21-item questionnaire that assesses severity of depression. Each item is scored from 0 to 3. The total score is categorized into 4 severity grades: minimal depression (0-13), mild depression (14-19), moderate depression (20-28), and severe depression (29-63).

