6.4 Study Time Intervals

Monthly Interval for Efficacy Endpoints

Monthly efficacy measurements will be calculated based on the subject's monthly IP dosing schedule defined below using eDiary data collected from beginning of the baseline phase (week -4 visit) up to week 76 (end of eDiary use). Any eDiary data occurring after EOS date will not be included in the analysis.

Study Phase	Assessment Timepoint	Start Date	End Date
Baseline Phase	Baseline	LogPad assignment date (Week -4 study visit)	Day prior to study day 1
Double-blind Treatment Phase	Week 4	
• Study Day 1	
• Week 4 dose date-1• Study day 28 if Week 4 dose is not received (either missed or IP discontinued prior to Week 4)
	Week 8	
• Week 4 dose date• Study day 29 if Week 4 dose is not received (either missed or IP discontinued prior to Week 4)	
• Week 8 dose date-1• Study day 56 if Week 8 dose is not received (either missed or IP discontinued prior to Week 8)
	Week 12	
• Week 8 dose date	
• Week 12 IP dose date-1• Study day 84 if Week 12

		
• Study day 57 if Week 8 dose is not received (either missed or IP discontinued prior to Week 8)	dose is not received (either missed or IP discontinued prior to Week 12)
	Week 16	
• Week 12 dose date• Study day 85 if Week 12 dose is not received (either missed or IP discontinued prior to Week 12)	
• Week 16 dose date-1• Study day 112 if Week 16 dose is not received (either missed or IP discontinued prior to Week 16)
	Week 20	
• Week 16 dose date• Study day 113 if Week 16 dose is not received (either missed or IP discontinued prior to Week 16)	
• Week 20 IP dose date-1• Study day 140 if Week 20 dose is not received (either missed or IP discontinued prior to Week 20)
	Week 24	
• Week 20 dose date• Study day 141 if Week 20 dose is not received (either missed or IP discontinued prior to Week 20)	
• Week 24 IP dose date-1• Study day 168 if Week 24 dose is not received (either missed or IP discontinued prior to Week 24)

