Open-label Treatment Phase	Week 28	
• The 1st OL dose day	
• Week 28 dose date-1• OLTP day 28 if Week 28 dose is not received (either missed or IP discontinued prior to Week 28)

	Week 32 or later when eDiary is used	
• Same rule as above	
--	--------------------------------------	--	--

Study Visit

Since the actual visit for a subject may not exactly coincide with their targeted visit date, the actual visit date is mapped to the study visit as follows.

Study Visit	Target Day	Study Day
Baseline		Please refer to Section 6.3 Baseline Assessment of the Study
Day 1	1	1
Week 4	29	16-43
Week 8	57	44-71
Week 12	85	72-99
Week 16	113	100-127
Week 20	141	128-155
Week 24	169	
• 156 to (week 24 OLTP dose date – 1) for subjects who receive OLTP dose at week 24• 156-183 for subjects who did not receive OLTP dose at week 24
Week 28	197	
• Week 24 OLTP dose date to 211 for subjects who receive OLTP dose at week 24• 184-211 for subjects who received at least one OLTP dose and did not

		receive OLTP dose at week 24 (e.g., first OLTP dose was postponed)
Week 32	225	212-239
Week 36 to Week 72	Following same monthly windowing as Week 32	
Safety follow-up	Based on visit name from RAVE or other source data	

Note:

If more than one visit (including the unscheduled visits, ie, CPEVENT = 'UNSCHED') fall within the same defined window, scheduled visit will be used regardless of the distance from the target day. Unscheduled visit will only be used when there is no scheduled visit in the defined window. The closest visit to the target day among the same type of visit (scheduled vs. unscheduled) will be considered for analysis. If two assessment dates are equidistant from the target date, the latter visit will be considered for analysis.

For safety analyses which are summarized by study phase, analysis windows will be set up based on study phase:

Study Phase	Start Time Point	End Time Point
Double-Blind Treatment Phase	Study Day 1 after the 1 st DB IP Dose	
First OL Dose Date for subjects who receive OL IP dose;Min(EOS Date, last IP dose date + 112 days) for subjects who do not receive any OL IP dose
Open-Label Treatment Phase	1 st OL IP Dose Date	Min(EOS Date, last OL IP dose date + 112 days)

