6.6 Arithmetic Calculations

Duration of Migraine

The number of years from the diagnosis date (DXDT) of migraine (migraine with aura or migraine without aura, whichever is earlier) to the date informed consent is signed.

If month or day of the diagnosis date is missing, follow the formula below to calculate the duration:

Observed portion	Missing portion	Formula to Calculate Duration
Year, Month, Day		(Informed Consent Day – DXDT)/365.25
Year, Month	Day	[Year(Informed Consent Day)-Year(DXDT)]+ [Month(Informed Consent Day)-Month(DXDT)]/12 *if it equals 0, add 1 month or 1/12 years (this is to avoid a disease duration of 0)
Year	Month, Day	[Year(Informed Consent Day)-Year(DXDT)] *if it equals 0, add 1 month or 1/12 years (this is to avoid a disease duration of 0)

Duration of DB IP Exposure

If subject enter into OL treatment phase,

Duration = Minimum (Last DB Dose Date + 27, First OL Dose Date - 1, EOS Date) – First DB Dose Date + 1

Otherwise,

Minimum (Last DB Dose Date + 27, EOS Date) – First DB Dose Date + 1

Duration of OLTP IP Exposure

Minimum (Last OLTP Dose Date + 27, EOS Date, Date of Data Cut-off) – First OLTP Dose Date + 1

Change from Baseline in Monthly Efficacy Measurement

The change from baseline in monthly efficacy measurement is the monthly efficacy measurement prior to the given time point minus the baseline monthly efficacy measurement. Please refer to the Monthly Intervals defined in [Section 6.4](#). For example, change from baseline in monthly migraine days at Week 24 will be calculated based on the following:

$$(\text{Monthly migraine days during the week 24 interval}) - (\text{monthly migraine days during the baseline phase})$$

If the baseline or post-baseline value is missing, then the change from baseline is set to missing.

Following Efficacy endpoints will be calculated as above:

- Change from baseline in monthly migraine days
- Change from baseline in monthly migraine attacks
- Change from baseline in monthly headache days
- Change from baseline in monthly migraine days with severe pain
- Change from baseline in monthly cumulative migraine hours
- Change from baseline in monthly cumulative migraine hours with severe pain
- Change from baseline in monthly acute medication use in days
- Change from baseline in monthly migraine-specific medication use in days
- Change from baseline in monthly average severity of migraine pain
- Change from baseline in monthly average migraine symptoms interference scale

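### The double-blind and open-label safety windows share the first open-label dose date, so an adverse event starting that day falls in both phases and, for placebo subjects, is charged to placebo

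*SAP*

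**What the plan says.** SAP 6.4 introduces its last table with the words "For safety analyses which are summarized by study phase, analysis windows will be set up based on study phase". For a subject who goes on to open-label treatment, the double-blind row ends at "First OL Dose Date for subjects who receive OL IP dose". The next row starts the open-label phase at "1 st OL IP Dose Date". The table has no rule for the shared day.

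Other parts of the documents bear on how that day is handled:

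- SAP 6.1.2 identifies treatment-emergent events "as determined by the flag indicating if the adverse event started prior to the first dose on the Adverse Events eCRF". That flag refers to the very first dose of investigational product, not to the first open-label dose.
- SAP 10.6 analyses safety by randomized treatment unless the wrong dose was received for the whole period of interest. SAP 10.6.1 tabulates adverse events by treatment group, separately for the two phases. Protocol 10.5.5 also requires the phases to be analysed separately.
- Protocol 7.2.24 places the first open-label dose after all week 24 procedures, and Protocol 7 has all procedures of a visit done on one day. The week 24 assessments and the first open-label dose therefore normally share a date.

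**The concern.** The shared day is a dosing day. For placebo subjects it is the day of their first AMG 334 dose. If the windows are applied by date, an event starting that afternoon satisfies the double-blind definition under placebo and the open-label definition as well. The same subject then appears in the numerator of both phase tables, and the placebo column contains an event that followed active drug. In the AMG 334 arms the day is likewise charged to the randomized dose, even where the open-label dose differs from it.

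What is at stake is the placebo reference column of the double-blind adverse event tables, chiefly for immediate events such as injection-site or hypersensitivity reactions. Incidence over the entire study is not affected, because a subject is counted once per event there.

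**Working it through.** The SAP states no figure for this point, so there is none to reproduce. The check compares date rules on the target schedule.

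**Inputs.** Dosing every 28 days from day 1 gives a week 20 dose on day 1 + 5 × 28 = 141 and a week 24 (first open-label) dose on day 1 + 6 × 28 = 169. These agree with the target days in the SAP 6.4 visit table. The placebo arm has about 131 subjects (SAP 3.1.1).

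**Step 1: overlap.** The double-blind safety window is days 1 to 169 and the open-label window starts on day 169. The intersection is day 169, exactly one day. If the open-label dose is 3 days early or late (day 166 or 172), the shared day moves with it and the overlap is still one day. Ending the double-blind window one day earlier gives days 1 to 168 and no overlap.

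**Step 2: how the SAP treats this boundary elsewhere.**

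| Rule | Last double-blind day when the first open-label dose is on day 169 |
|---|---|
| Safety window, SAP 6.4 | 169 |
| Week 24 efficacy interval, SAP 6.4 (dose date minus 1) | 168 |
| Week 24 visit window, SAP 6.4: "156 to (week 24 OLTP dose date – 1) for subjects who receive OLTP dose at week 24" | 168 |
| Double-blind exposure, SAP 6.6: "Minimum (Last DB Dose Date + 27, First OL Dose Date - 1, EOS Date" | min(141 + 27, 169 − 1) = 168 |

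The efficacy interval has the same end when there is no dose: "Study day 168 if Week 24 dose is not received". Three parallel rules subtract the day and the safety window does not, which suggests an omission.

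**Step 3: can anything else separate the events?** The eCRF flag concerns only the first dose of all. The partial-date exceptions in SAP 9.3.1 refer only to Study Day 1. Among the attributes required in Protocol 9.2.1, onset is recorded as a date. None of these divides week 24 events into pre-dose and post-dose.

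**Step 4: size.** Subject incidence in SAP 6.6 divides by the number of subjects entering the period. If all 131 placebo subjects are dosed, one additional subject adds 1/131 = 0.76 percentage points.

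The documents give no rate of events starting on a dosing day. As an illustration only, assume that 80 to 100% of placebo subjects enter the open-label phase (0.80 × 131 = 105, up to 131) and that 1 to 5% of them have a new event that day:

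- Low end: 105 × 0.01 = 1.05 subjects, or 1.05/131 = 0.8 points.
- High end: 131 × 0.05 = 6.55 subjects, or 6.55/131 = 5.0 points.

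Both rates are assumptions. The counts also treat every event as post-dose and none as a repeat. A subject who already had the same event during the double-blind phase adds nothing.

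**The case against.** The table heads its columns as time points rather than dates, and its double-blind row begins after the first dose within Study Day 1. One could therefore read the first open-label dose as a moment of hand-over. The inclusive wording in SAP 6.1.2, "up to and including 112 days after the end of investigational product", governs the 112-day tail and not the phase boundary. It is true that inclusion of the shared day is inferred and not written. But the open-label boundary has no before-or-after-dose qualifier like the one on the double-blind start, and events recorded by date cannot be split by an unstated moment. The text needs a rule on either reading.

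A reader might also infer that the mismatch with double-blind exposure distorts the exposure-adjusted rates, with an event in a numerator but its time missing from the denominator. The documents do not support that. SAP 6.6 gives those rates their own time at risk: up to the first event for subjects with one, and up to the last follow-up assessment for the others. The exposure duration feeds the descriptive summary in SAP 10.6.7. Nor are the two meant to match. Without an open-label dose, exposure ends 27 days after the last dose and the safety window at 112 days.

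Nor do the documents show a material bias in the safety comparison:

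- The extra day is added in every arm, so only a difference between arms changes the contrast.
- Placebo subjects already have six double-blind dosing days with three injections each, so injection reactions are already represented in their incidence.
- Protocol 2.2 gives a median time to peak concentration of 4 to 11 days, which makes same-day events driven by systemic levels less likely.
- SAP 10.6 plans no safety testing between groups.

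These points limit the size of the problem. They do not settle which phase the day belongs to.

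**Conclusion.** The point holds as a boundary error in the adverse event windows. Applied by date, SAP 6.4 puts an event starting on the first open-label dose date in both phases, and it can place a placebo subject's reaction to a first AMG 334 dose in the placebo double-blind column. The effect is one day per subject entering the open-label phase, at about 0.8 percentage points for each new placebo subject. How many such subjects there would be cannot be derived from the documents.

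The conclusion assumes that the windows are programmed on calendar dates, as the table is written. It concerns descriptive summaries only; no test and no efficacy result changes. It is a minor correction, best made before unblinding.

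**What to change.** For adverse events only, end the double-blind window on the day before the first open-label dose. Assign events starting on the first open-label dose date to the open-label phase unless onset is documented as before that dose, so that each event is counted in one phase.

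Do not apply the subtraction to the whole table. The table also governs the other safety summaries by phase, and a blanket change would push the pre-dose week 24 laboratory, vital sign, ECG and C-SSRS results out of the double-blind phase. State separately that such assessments made on that date before dosing belong to the double-blind phase. SAP 6.3 already assumes that same-day baseline measurements precede the dose, so there is a precedent. Align the week 24 visit window accordingly, because it now excludes the first open-label dose date and maps it to week 28.

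The cost is a few sentences in SAP 6.4 and the matching programming, with no new data needed for the date rule. The downside is that a few pre-dose events without a recorded onset time may be placed in the open-label phase.

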7. STUDY PROCEDURES

Refer to the Schedule of Assessments ([Table 2 -Table 4](#)) for an outline of the procedures required at each study visit.

Refer to the applicable supplemental manuals (eg, laboratory, ECG) for detailed collection and handling procedures.

Allowable windows for visits are the following:

- Each study visit during the 24-week double-blind treatment phase and safety follow-up has a window of ± 3 consecutive calendar days.
- The day 1 visit (randomization day) has a window of 0, +7 consecutive calendar days; the day 1 visit must occur 28 to 35 days after the week -4 visit date.
- Each study visit during the 76-week **OLTP** has a window of ± 4 consecutive calendar days.
- All study visit target dates are to be calculated from the day 1 visit date.
- All study procedures for a given study visit are to be completed on the same day.
- Each PK substudy sampling has a window of ± 3 consecutive calendar days.

Refer to the Schedule of Assessments ([Table 4](#)) for an outline of the procedures required at each study visit in the CHU substudy.

Investigators are responsible for ensuring that all study procedures are performed as specified in the protocol.

Study visits should be conducted without additional non-protocol therapies and subjects should be reminded about the investigational nature of the study drug.

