9.2 Safety Event Reporting Procedures

9.2.1 Reporting Procedures for Adverse Events and Adverse Device Effects That do not Meet Serious Criteria

The investigator is responsible for ensuring that all adverse events **and adverse device effects (including the OLTP and CHU substudy)** observed by the investigator or reported by the subject that occur after the first dose of investigational product through the end of the safety follow-up visit (16 weeks after the last dose of investigational product) are reported using the Event CRF (eg, Adverse Event Summary), including events that are reported to the Event Adjudication Committee for adjudication.

The investigator must assign the following adverse event attributes:

- adverse event diagnosis or syndrome(s), if known (if not known, signs or symptoms),
- dates of onset and resolution (if resolved),

- severity and/or toxicity,
- assessment of relatedness to investigational product (**AMG 334/placebo**), and/or **the Amgen medical devices (pre-filled syringe or the AI/Pen)**, and/or **study-mandated procedure/study activity**, and
- action taken.

The adverse event grading scale used will be the CTCAE. The grading scale used in this study is **available at the following location:**

http://ctep.cancer.gov/protocolDevelopment/electronic_applications/ctc.htm.

During the double-blind treatment period, the investigator must assess whether the adverse event is possibly related to the investigational **medicinal** product (**AMG 334/placebo**). This relationship is indicated by a “yes” or “no” response to the question: “Is there a reasonable possibility that the event may have been caused by the investigational **medicinal** product (**AMG 334/placebo**)?”

During the OLTP and the CHU substudy, the investigator must assess whether the adverse event is possibly related to **AMG 334**. This relationship is indicated by a “yes” or “no” response to the question: “Is there a reasonable possibility that the event may have been caused by **AMG 334**?”

During the OLTP and the CHU substudy, the investigator must assess whether the adverse event is possibly related to the prefilled syringe or AI/Pen (investigational medical devices used to administer **AMG 334**). The relationship is indicated by a “yes” or “no” response to the question: Is there a reasonable possibility that the event may have been caused by the investigational medical devices?

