Entire Study	Study Day 1 after the 1 st DB IP Dose	Min(EOS Date, last IP dose date + 112 days)

Note: all antibody data will be included in antibody analysis.

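### SAP 6.4 closes the by-phase safety windows at last dose + 112 days, so a permitted follow-up visit on days 113 to 115 falls outside the phase summaries that use the date cut

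*SAP*

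**What the plan says.** SAP 6.4 sets date windows for safety analyses summarised by study phase.

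- **Open-label phase:** ends at "Min(EOS Date, last OL IP dose date + 112 days".
- **Double-blind phase, subjects with no open-label dose:** ends at "Min(EOS Date, last IP dose date + 112 days) for subjects who do not receive any OL IP dose".
- **Entire study:** ends at "Min(EOS Date, last IP dose date + 112 days".

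The one exemption noted there is that "all antibody data will be included in antibody analysis". The visit table in the same section assigns the safety follow-up by its recorded visit name, with no day range. The SAP does not say which rule prevails when the two disagree.

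The protocol synopsis and Protocol 7.2.26 place the follow-up visit 16 weeks after the last dose. Protocol 7 gives the tolerance: "Each study visit during the 24-week double-blind treatment phase and safety follow-up has a window of ± 3 consecutive calendar days". The same list adds that "All study visit target dates are to be calculated from the day 1 visit date".

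For adverse events, SAP 6.1.2 counts an event as treatment-emergent "up to and including 112 days after the end of investigational product (16 weeks after the last dose of IP"), or to end of study if earlier. Protocol 9.2.1 collects events "through the end of the safety follow-up visit (16 weeks after the last dose of investigational product").

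**The concern.** The cut-off equals the nominal visit date and leaves no room for the visit window. A subject seen one to three days after target has complied with the protocol, yet the visit is dated after the phase has closed for analysis.

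Protocol 7.2.26 schedules chemistry, hematology, vital signs, C-SSRS, antibodies and adverse event review at this visit. For open-label completers it is the assessment about 16 weeks after dosing. If the rule is programmed as written, appointment timing decides whose late off-drug laboratory and C-SSRS results reach the by-phase tables. Where the visit-name rule and the date rule disagree, two programmers could produce different tables from the same data.

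**Working it through.** **Inputs**
- Follow-up target: 16 weeks after last dose (Protocol synopsis; 7.2.26).
- Follow-up window: ± 3 days (Protocol 7).
- Open-label visit window: ± 4 days (Protocol 7).
- Cut-off: the earlier of EOS and last dose + 112 days (SAP 6.4).
- EOS: the subject's last date of participation (SAP 6.2).

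**1. The plan's own figure.** 16 × 7 = 112 days, so the SAP's equation of 112 days with 16 weeks reproduces.

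**2. Permitted visit days.** 112 − 3 = 109 to 112 + 3 = 115, which is seven days.

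**3. Apply the cut.** Take a visit on day 113, 114 or 115. EOS is then at least day 113, so min(EOS, 112) = 112 and the visit is outside. Days 109 to 112 are inside. The share of permitted days lost is 3/7 = 0.43. This reads the end point as inclusive, as SAP 6.1.2 does for adverse events. Read as exclusive, day 112 is lost as well (4 of 7).

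**4. If targets are counted from Day 1.** Take the last dose at Week 96 ± 4 days and the follow-up at Week 112 ± 3 days:
- shortest gap: (784 − 3) − (672 + 4) = 781 − 676 = 105 days;
- longest gap: (784 + 3) − (672 − 4) = 787 − 668 = 119 days;
- of the 9 × 7 = 63 combinations of offsets, 1 + 2 + 3 + 4 + 5 + 6 + 7 = 28 exceed 112 days, and 28/63 = 0.44.

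The SAP's own schedule, with last dose at Week 72 and end at Week 88, has the same 16-week spacing and gives the same range.

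**5. Which outputs are touched**

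| Output | SAP section | Effect of a visit on days 113 to 115 |
|---|---|---|
| ANC shift, by phase | 10.6.2 | Outside the window |
| Liver-test abnormality incidence, by phase | 10.6.2 | Outside the window |
| C-SSRS counts and shifts, by phase | 10.6.4 | Outside the window |
| ANC/ALT/AST change, by visit and phase | 10.6.2 | Visit name includes it, date cut excludes it |
| Vital signs over time | 10.6.3 | No phase stated; not clearly affected |
| Antibodies | 6.4, 10.6.6 | Exempt |
| Adverse events with onset by day 112 | 6.1.2 | Still counted, even if reported late |

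Vital signs are marked as not clearly affected, rather than safe, because Protocol 10.5.5 says in general terms that safety analyses are done separately by phase.

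**6. Check of the fix.** Replace the end point with min(EOS, max(last dose + 112, visit date)). For a visit on day 115 with EOS 115 this gives 115, so the visit is included. For a visit on day 109 with EOS 109 it gives 109, as now. No permitted day is lost. A fixed last dose + 115 also covers days 113 to 115, but under step 4 it would miss days 116 to 119.

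Version drift does not explain the mismatch. The SAP was written to Protocol 1.0, and the superseded footnote in the amendment log carries the same ± 3 days.

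**The case against.** The strongest reply is that a fixed post-dose period is a legitimate pre-specified choice. It gives every subject the same upper limit on follow-up. Protocol 7.2.23, 7.2.24 and 7.2.26 end adverse event collection at 16 weeks after the last dose, which is exactly 112 days, and the SAP's serious adverse event definition runs to end of study. This stands for treatment-emergent events: only onsets after day 112 are lost, and the 112-day limit in SAP 6.1.2 can be defended.

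The reply can add that visit-name mapping already rescues the follow-up visit. That holds in part. It makes the by-visit laboratory table ambiguous rather than clearly short of data. It does not reach the ANC shift, liver-test or C-SSRS phase summaries, which are not tied to a named visit.

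The consequences are also limited. For subjects who enter the open-label phase, the double-blind window closes at the first open-label dose, so their placebo-controlled safety data are untouched. SAP 10.6 plans no between-group safety tests. This is a fair limit on importance, but it gives no reason to discard compliant measurements.

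A reader might infer that this is the only planned safety assessment after treatment. The documents do not support that: Week 100/ET follows the last scheduled dose at Week 96, and subjects who stop double-blind product early keep attending visits to Week 24.

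**Conclusion.** The mismatch holds for visit-based measurements. As written, SAP 6.4 excludes three of the seven permitted follow-up days from the phase summaries that rely on the date cut, and it leaves one laboratory table with two conflicting rules. It is worth correcting, but it is a limited reporting defect. It does not bear on efficacy.

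A reader might infer that 43% or 44% of follow-up visits will be lost, or that some loss is certain. Neither follows. Both percentages assume that visits (and, for 44%, doses) are spread evenly over their windows, and the documents give no timing data. The share falls if sites keep to the target date, and it could be zero, because late visits are permitted but not required. The 44% also applies the general Day 1 anchor to a visit that the protocol repeatedly ties to the last dose; it is used here only to test the fix.

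A reader might also infer that all safety data from a late visit are lost, or that the treatment-emergent definition is wrong. The table and the adverse event passages cited above do not support either.

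**What to change.** In SAP 6.4, for visit-based safety measurements, end the open-label, entire-study and no-open-label double-blind windows at the later of last IP dose + 112 days and the safety follow-up visit date, capped at EOS. State that the scheduled follow-up visit identified by visit name is included; this also settles the by-visit, by-phase laboratory table. Do not use a fixed + 115 days, which is not equivalent and could still miss visits if targets run from Day 1.

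The 112-day treatment-emergent period in SAP 6.1.2 may stay as a pre-specified choice. If the sponsor prefers to align it with Protocol 9.2.1, the protocol's adverse event collection passages (7.2.23, 7.2.24 and 7.2.26 against 9.2.1) should be reconciled first.

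The cost is one SAP definition and no new data. The small downside is that follow-up will differ by a few days between subjects.
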